1. INTRODUCTION

1.1 BACKGROUND

Aramchol is a novel conjugate of cholic acid (bile acid) and arachidic acid (saturated fatty acid), linked by a stable amide group. It is in development for treatment of nonalcoholic steatohepatitis (NASH) and fibrosis. Aramchol affects stearoyl coenzyme A desaturase 1, a key liver enzyme involved in regulating lipid metabolism. In animal models of NASH, it reduces steatosis, ballooning, inflammation, and fibrosis by down-regulation of stearoyl coenzyme A desaturase 1 expression in hepatocytes and hepatic stellate cells.

Aramchol is highly lipophilic and pharmacokinetic (PK) studies in humans show that plasma concentrations increase less than proportionally to dose due to poor absorption. Its mean terminal phase half-life ($t_{1/2}$) is approximately 3 days but most of the drug is cleared with a $t_{1/2}$ of about 35 hours and steady state on repeat dosing is achieved within 7 to 10 days. Aramchol is secreted in bile and is excreted in feces. [REDACTED]

[REDACTED]

[REDACTED]

[REDACTED] Two

Phase 2 clinical studies have been completed including a placebo-controlled study in which subjects with NASH were treated for 52-weeks. Significantly more subjects who received aramchol 600 mg daily showed NASH resolution without worsening of fibrosis and a larger proportion of subjects showed at least a 1-point improvement in fibrosis score without worsening of steatohepatitis.

1.2 RATIONALE FOR STUDY

This study will compare the effect of varying degrees of hepatic impairment on the PK, safety, and tolerability of a single oral dose of 600 mg (2×300 -mg tablets) aramchol in

Part 1 and multiple oral doses not to exceed 300 mg twice daily for 11 days and a single 300 mg AM dose on Day 12 in Part 2 with healthy subjects.

Hepatic impairment associated with cirrhosis may develop in subjects with NASH. Therefore, it is important to assess the effect of hepatic impairment on the PK and hence dosage requirements and safety of aramchol.

1.3 RATIONALE FOR DOSE SELECTION

A single oral dose of 600 mg aramchol in Part 1 and multiple oral doses not to exceed 300 mg aramchol twice daily for 11 days and a single AM dose on Day 12 in Part 2 will be evaluated in this study based on the recommendations provided in the US Food and Drug Administration (FDA) Guidance for Industry, Pharmacokinetics in Patients with Impaired Hepatic Function: Study Design, Data Analysis, and Impact on Dosing and Labeling (DHHS 2003). Though single doses up to 900 mg have been studied in healthy subjects and tolerated well, the single dose of 600 mg represents the highest dose likely to be used and was the daily dose administered in the Phase 2b study. The multiple dose of 300 mg twice daily has been well tolerated by healthy subjects for 10 days and is the dose to be taken daily by subjects participating in a Phase 3 clinical trial.

The duration of multiple dosing is based on the apparent plasma elimination half-life of about 35 hours and time taken to reach steady state of about 7 days in healthy subjects. A duration of 10 days was chosen to ensure steady state has been achieved by all the healthy subjects and an additional 2 days is considered appropriate for subjects with hepatic impairment owing to the possibility of reduced clearance in this population.

2. STUDY OBJECTIVES

2.1 PRIMARY OBJECTIVE

The primary objective of this study is to compare the PK profile of aramchol administered orally in subjects with hepatic impairment with that of healthy subjects.

2.2 SECONDARY OBJECTIVE

The secondary objective of this study is to assess the safety and tolerability of aramchol administered orally in subjects with hepatic impairment.

3. STUDY DESIGN

This is a Phase 1, multicenter, open-label, 2-part, single- and multiple-dose study designed to assess the effect of hepatic insufficiency on the PK of aramchol.

Each part of the study will consist of a screening period, a check-in day, a treatment period, and an end-of-study (EOS) visit.

In Part 1 (single-dose), up to 48 subjects are planned: 8 subjects each in the mild (Cohort A), moderate (Cohort B), and severe (Cohort C) hepatic impairment cohorts and 8 to 24 healthy control subjects with normal hepatic function (Cohort D). Enrollment of 8 subjects with mild hepatic impairment (Cohort A) will proceed only if there is evidence of reduced clearance of aramchol in Cohort B. At screening, subjects will be assigned to a study cohort according to the Child-Pugh classification system as follows:

Cohort	Hepatic Condition	Child-Pugh Grade	Number of Subjects
A ^(a)	Mild impairment	Class A (Score of 5 to 6)	8
B	Moderate impairment	Class B (Score of 7 to 9)	8
C	Severe impairment	Class C (Score of 10 to 15)	8
D	Healthy (control)	—	8 to 24

^(a) Enrollment of subjects into Cohort A will only proceed if there is evidence of reduced clearance of aramchol in Cohort B.

Healthy control subjects (Cohort D) will be matched with hepatically impaired subjects (Cohorts A, B, and C) according to gender, age (± 10 years), and body mass index (BMI) ($\pm 20\%$).

Safety data and PK profiles of aramchol from at least 4 subjects with moderate hepatic impairment (Cohort B) will be obtained and reviewed while enrollment to this cohort continues. These 4 subjects in Cohort B must demonstrate satisfactory safety (no serious AEs [SAEs] or severe AEs related to aramchol) and PK results for up to 4 days after dosing before enrollment of subjects with severe hepatic impairment (Cohort C) is initiated. Two subjects with severe hepatic impairment must demonstrate satisfactory safety and tolerability (no SAEs or severe AEs related to aramchol) for up to 4 days after dosing before the remaining subjects with severe hepatic impairment may be dosed.

Enrollment of subjects to Cohort A (mild hepatic impairment) will proceed only if there is evidence of reduced clearance of aramchol in the first 4 subjects in Cohort B (moderate hepatic impairment), defined as a reduction in apparent total oral clearance (CL/F) of greater than 30% compared with values in historical healthy control subjects.

In Part 2, a cohort of at least 8 subjects comprising of mild and moderate or moderate and severe hepatic impairment subjects will be administered aramchol as multiple doses to obtain the PK profile of aramchol at steady state. A decision on the severity of hepatic impairment of subjects to participate in Part 2 (multiple-dose) will be made by the sponsor based on the available safety and PK results from Part 1 (single-dose).

Healthy control subjects will be matched with the hepatically impaired subjects according to gender, age (± 10 years), and BMI ($\pm 20\%$).

Single Dose (Part 1):

On Day 1, subjects will receive a single oral dose of 600 mg aramchol administered with 240 mL of water in the morning, after an overnight fast of at least 10 hours, and approximately 30 minutes after consuming a standardized breakfast. Subjects will remain fasted except for water for 2 hours after dosing. During the study, subjects may consume water on an ad libitum basis. Hepatically impaired subjects will receive a diet standardized for hepatic impairment and healthy control subjects will receive a similar diet.

Serial blood samples for PK analysis of aramchol concentrations in plasma will be collected before dosing (0 hour) and up to 168 hours for healthy subjects and 240 hours for hepatically impaired subjects after administration of aramchol.

Subjects will be confined to the clinical site from Day -1 until discharge on Day 8 for healthy control subjects and on Day 11 for hepatically impaired subjects. The duration of the study, excluding screening, is approximately 23 days.

Multiple Dose (Part 2):

Multiple dosing will involve twice daily (approximately 12 hours apart) oral administration of aramchol for 11 days with a single AM dose on Day 12 to achieve steady state. The dosage will not exceed 300 mg twice daily but may be adjusted to give lower exposure depending on review of available data on any reduction in clearance associated with hepatic impairment seen with single doses in Part 1. Subjects will consume a standardized meal 30 minutes prior to the AM and PM doses of aramchol. Subjects will remain fasted except for water for 2 hours after dosing. During the study, subjects may consume water on an ad libitum basis. Hepatically impaired subjects will receive a diet standardized for hepatic impairment and healthy control subjects will receive a similar diet.

Blood samples for analysis of aramchol concentrations in plasma will be collected before the AM dose on Days 1, 4, 8, 9, 10, 11, and 12 and at intervals to 12 hours after the AM dose on

Day 12. Samples of plasma will also be stored for analysis of metabolites pending results of a mass balance study.

Subjects will be confined to the clinical site from Day –1 until discharge on Day 13. The duration of the study, excluding screening, is approximately 28 days.

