7.5 INTERIM ANALYSES

No formal interim analyses will be performed in this study.

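### Cohort A entry is defined on the first 4 Cohort B subjects only, with no stated re-check when all 8 are available and two sentences that do not carry the limit of 4

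*Combined protocol and SAP*

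**What the plan says.** Section 3 (Study Design), repeated in the Synopsis, contains one sentence that defines the entry rule for the mild cohort. Enrollment to Cohort A "will proceed only if there is evidence of reduced clearance of aramchol in the first 4 subjects in Cohort B (moderate hepatic impairment"), with reduced clearance "defined as a reduction in apparent total oral clearance (CL/F) of greater than 30% compared with values in historical healthy control subjects".

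Two other statements in Section 3, also in the Synopsis, name Cohort B without limiting the evidence to 4 subjects. One stands in the paragraph before the cohort table. The other is the table footnote: "Enrollment of subjects into Cohort A will only proceed if there is evidence of reduced clearance of aramchol in Cohort B".

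The same section plans "8 subjects each in the mild (Cohort A), moderate (Cohort B), and severe (Cohort C) hepatic impairment cohorts", and says that data from at least 4 Cohort B subjects "will be obtained and reviewed while enrollment to this cohort continues". All 8 therefore become available later.

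Section 7.5 states: "No formal interim analyses will be performed in this study". Section 7.1 says that the sample size does not rest on a power calculation. No section names the summary statistic for the rule, a precision requirement, the historical data set, or what happens when Cohort B is complete.

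**The concern.** The operative definition compares 4 people with a fixed 30% cut-off. Another 4 subjects in the same cohort are dosed and assayed in any case, yet the defined rule does not use them. If the first 4 fall just short and all 8 exceed 30%, the defining sentence keeps Cohort A closed while the two broader sentences would let it open. The choice between them would then be made in an open-label study with the data in view.

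At stake is the single-dose mild cohort. Without it, the Section 7.3.1 ANOVA has no mild versus matched-normal comparison in Part 1, and the sponsor chooses the Part 2 severity mix without single-dose data in mild impairment.

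**Working it through.** The documents give no error rate for this rule, so there is no figure of theirs to reproduce.

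**Inputs from the documents.** First look n = 4; full Cohort B n = 8; cut-off ratio 0.70 (a reduction above 30%); historical healthy reference of unstated size and variance.

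**Assumptions, not in the documents.** Log-normal CL/F; between-subject CV of 30% to 60%; geometric mean as the statistic; reference known without error; true reduction 40% (ratio 0.60).

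**Miss at a single look.** With s = √ln(1 + CV²),

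P(not opened) = Φ[(ln 0.60 − ln 0.70) / (s/√n)], where ln 0.60 − ln 0.70 = −0.154.

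At CV 30%, s = 0.294, the standard error for n = 4 is 0.147, z = −1.05, and the miss is 14.7%. At CV 60%, s = 0.555, the standard error is 0.277, z = −0.56, and the miss is 28.9%.

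**Look at 4, then re-check at 8, same reference.** The two log means have correlation √(4/8) = 0.71. The miss is the bivariate normal probability that both looks fall short.

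| CV | Miss, 4 only | Miss, 8 only | Miss, 4 then 8 |
|---|---|---|---|
| 30% | 14.7% | 6.9% | 4.5% |
| 40% | 21.2% | 12.9% | 8.7% |
| 50% | 25.7% | 17.8% | 12.2% |
| 60% | 28.9% | 21.6% | 15.0% |

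The re-check recovers 1 − 4.5/14.7 = 69% of the misses at CV 30% and 1 − 15.0/28.9 = 48% at CV 60%.

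**Sensitivity of the first look.**
- CV 20%: miss 6.0%. CV 80%: 33.1%.
- True 50% reduction, CV 30% to 60%: 1% to 11%.
- True 30% reduction: 50% at any CV.
- Arithmetic mean instead of geometric: 13% to 25%. Median: 18% to 33%.
- Historical reference estimated from 8 to 24 subjects (standard error s√(1/4 + 1/m)): 17% to 20% at CV 30%, 30% to 33% at CV 60%.

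**Cost in unneeded opening, true 15% reduction.** These use the same formulas with ln 0.85. For a re-check of 8 against 8 matched controls, the standard error is s√(1/8 + 1/8) = s/2. That is the same as for 4 subjects against a known reference, and the correlation with the first look is 0.5.

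| CV | 4 only | Re-check, historical | Re-check, matched controls |
|---|---|---|---|
| 30% | 9.3% | 10.4% | 15.7% |
| 40% | 15.7% | 18.3% | 25.2% |
| 50% | 20.6% | 24.6% | 32.0% |
| 60% | 24.2% | 29.3% | 36.9% |

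The historical version adds 1.1 to 5.1 points and the matched version 6.4 to 12.7. At a true 40% reduction, opening is 95%, 91%, 88% and 85% with the historical reference, and 94%, 91%, 87% and 85% with matched controls, so the matched version gains nothing. With no true reduction, the historical version moves opening from 0.8% to 0.8% at CV 30% and from 9.9% to 11.1% at CV 60%.

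**The case against.** The strongest reply is that a one-look rule for an optional cohort, in a study that disclaims a power calculation, is a resource decision the sponsor is free to make. That is fair as far as it goes. It does not explain why the defined rule should ignore data already planned, or why three sentences in one section differ on which subjects count.

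Four stronger readings are tempting, and the documents do not support them.

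- *A failed first look closes Cohort A for good.* No section says the decision is final, and the two broader sentences leave room for a later one. The documents are silent on this, which is why the sentences need reconciling.
- *A failed first look leaves no data in mild impairment.* Section 3 allows Part 2 to enroll mild and moderate subjects, and nothing makes this depend on Cohort A having opened. What is lost is the single-dose mild cohort.
- *The reduction in moderate impairment goes unseen, or the primary objective fails.* Section 7.3.1 still compares Cohort B with its matched controls on log AUC and Cmax. The primary objective names no Child-Pugh class.
- *The mild class is the one most likely to be treated.* The documents do not say so. Section 1.2 says only that hepatic impairment associated with cirrhosis may develop in NASH.

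It also stands that a re-check gives a second chance to open when the true effect is small. The cost is real but modest if the reference is unchanged.

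**Conclusion.** The point holds in a limited form. The only defining sentence uses the first 4 of 8 subjects, no re-check is described, and the neighboring sentences do not carry the same limit. Following the defined rule can therefore keep the mild cohort closed when the completed Cohort B would meet the same criterion.

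For a true 40% reduction this happens at the first look about 15% to 29% of the time. That range is not a property of the plan. It depends on an assumed CV of 30% to 60%, log-normal CL/F, a geometric mean and an error-free historical reference. A smaller CV or a larger true effect shrinks it (6% at CV 20%; 1% to 11% at a true 50% reduction), and an uncertain reference enlarges it. Even the use of a point estimate is inferred, because the rule names no statistic.

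The preference for the historical reference over matched controls at the re-check also rests on that reference being well estimated. With m historical subjects the standard error at 8 is s√(1/8 + 1/m), which reaches s/2 when m = 8.

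This is a worthwhile and inexpensive improvement. It does not undermine the trial's main comparisons.

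**What to change.** Before the first 4 Cohort B results are reviewed:

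1. Reconcile the three sentences in Section 3, and their copies in the Synopsis, so that they name the same subjects.
2. State the statistic and identify the historical healthy data set.
3. Keep the look at 4 and add: *If the criterion is not met in the first 4 subjects, the same criterion (geometric mean CL/F against the same historical healthy reference) will be re-applied to all 8 Cohort B subjects before Cohort A is closed.*

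Do not move the re-check to the 8 matched controls. Under the assumptions above, that adds about 6 to 13 points of opening at a true 15% reduction, with no gain in detection at a true 40% reduction. The matched comparison is made in the final analysis anyway.

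The change needs no subjects beyond the 48 planned for Part 1 and no extra assays. The price is a possibly later opening of Cohort A and about 1 to 5 points more opening at a true 15% reduction. In return, the miss at a true 40% reduction falls from about 15% to 29% to about 5% to 15%.

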The secondary objective of this study is to assess the safety and tolerability of aramchol administered orally in subjects with hepatic impairment.

STUDY DESIGN:

This is a Phase 1, multicenter, open-label, 2-part, single- and multiple-dose study designed to assess the effect of hepatic insufficiency on the PK of aramchol.

Each part of the study will consist of a screening period, a check-in day, a treatment period, and an end-of-study (EOS) visit.

In Part 1 (single-dose), up to 48 subjects are planned: 8 subjects each in the mild (Cohort A), moderate (Cohort B), and severe (Cohort C) hepatic impairment cohorts and 8 to 24 healthy control subjects with normal hepatic function (Cohort D). Enrollment of 8 subjects with mild hepatic impairment (Cohort A) will proceed only if there is evidence of reduced clearance of aramchol in Cohort B. At screening, subjects will be assigned to a study cohort according to the Child-Pugh classification system as follows:

Cohort	Hepatic Condition	Child-Pugh Grade	Number of Subjects
A ^(a)	Mild impairment	Class A (Score of 5 to 6)	8
B	Moderate impairment	Class B (Score of 7 to 9)	8
C	Severe impairment	Class C (Score of 10 to 15)	8
D	Healthy (control)	—	8 to 24

^(a) Enrollment of subjects into Cohort A will only proceed if there is evidence of reduced clearance of aramchol in Cohort B.

Healthy control subjects (Cohort D) will be matched with hepatically impaired subjects (Cohorts A, B, and C) according to gender, age (± 10 years), and body mass index ($\pm 20\%$).

Safety data and PK profiles of aramchol from at least 4 subjects with moderate hepatic impairment (Cohort B) will be obtained and reviewed while enrollment to this cohort continues. These 4 subjects in Cohort B must demonstrate satisfactory safety (no serious adverse events [AEs] or severe AEs related to aramchol) and PK results for up to 4 days after dosing before enrollment of subjects with severe hepatic impairment (Cohort C) is initiated. Two subjects with severe hepatic impairment must demonstrate satisfactory safety and tolerability (no serious AEs or severe AEs related to aramchol) for up to 4 days after dosing before the remaining subjects with severe hepatic impairment may be dosed.

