Enrollment of subjects into Cohort A (mild hepatic impairment) will proceed only if there is evidence of reduced clearance of aramchol in the first 4 subjects in Cohort B (moderate hepatic impairment), defined as a reduction in apparent total oral clearance (CL/F) of greater than 30% compared with values in historical healthy control subjects.

In Part 2, a cohort of at least 8 subjects comprising of mild and moderate or moderate and severe hepatic impairment subjects will be administered aramchol as multiple doses to obtain the PK profile of aramchol at steady state. A decision on the severity of hepatic impairment of subjects to participate in Part 2 (multiple-dose) will be made by the sponsor based on the available safety and PK results from Part 1 (single-dose).

Healthy control subjects will be matched with the hepatically impaired subjects according to gender, age (± 10 years), and body mass index ($\pm 20\%$).

Single Dose (Part 1):

On Day 1, subjects will receive a single oral dose of 600 mg aramchol administered with water in the morning, after an overnight fast of at least 10 hours, and approximately 30 minutes after consuming a standardized breakfast. Subjects will remain fasted except for water for 2 hours after dosing. During the study, subjects may consume water on an ad libitum basis. Hepatically impaired subjects will receive a diet standardized for hepatic impairment and healthy control subjects will receive a similar diet.

Serial blood samples for PK analysis of aramchol concentrations in plasma will be collected before dosing (0 hour) and up to 168 hours for healthy subjects and 240 hours for hepatically impaired subjects after administration of aramchol.

Subjects will be confined to the clinical site from Day -1 until discharge on Day 8 for healthy control subjects and on Day 11 for hepatically impaired subjects. The duration of the study, excluding screening, is approximately 23 days.

Multiple Dose (Part 2):

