5. STUDY TREATMENTS

5.1 TREATMENTS ADMINISTERED

All doses of study drug will be administered by mouth with 240 mL of room temperature water. During the study, subjects may consume water on an ad libitum basis.

Hepatically impaired subjects will receive a diet standardized for hepatic impairment and healthy control subjects will receive a similar diet. Subjects should receive these meals at the same time during each part of the study.

Single Dose (Part 1):

On Day 1, all subjects will receive a single oral dose of 600 mg (2 × 300-mg tablets) aramchol in the morning, after an overnight fast of at least 10 hours and approximately 30 minutes after a standardized breakfast.

Multiple Dose (Part 2):

Starting on Day 1, all subjects will receive an oral dose of aramchol that will not exceed 300 mg twice daily (approximately 12 hours apart) for 11 days and a single AM dose on Day 12 approximately 30 minutes after a standardized meal. The dose may be adjusted to give lower exposure depending on the review of available data on any reduction in clearance associated with hepatic impairment seen with single doses in Part 1.

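### Does the rule that opens the mild cohort need a named historical dose and summary statistic before it can be used?

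*Combined protocol and SAP*

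**What the plan says.** The synopsis and Section 3 (Study Design) give the condition for enrolling Cohort A at two levels of detail. The sentence beside the cohort table says that enrolment "will proceed only if there is evidence of reduced clearance of aramchol in Cohort B", and the table footnote says that it "will only proceed if there is evidence of reduced clearance of aramchol in Cohort B". A later paragraph of the same section requires "evidence of reduced clearance of aramchol in the first 4 subjects in Cohort B" and defines this as a reduction in "CL/F) of greater than 30% compared with values in historical healthy control subjects".

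Three other statements bear on the reference:

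- Section 1.1 reports that "plasma concentrations increase less than proportionally to dose due to poor absorption".
- Section 1.3 says that "single doses up to 900 mg have been studied in healthy subjects" and, separately, that "The multiple dose of 300 mg twice daily has been well tolerated by healthy subjects for 10 days".
- Section 5.1 fixes the Part 1 dose: "On Day 1, all subjects will receive a single oral dose of 600 mg", given after breakfast.

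Section 6.1 lists CL/F among the single-dose parameters of Part 1 and not among the Day 12 parameters of Part 2. Section 7.3.1 plans arithmetic means and medians for all PK parameters, and adds geometric means only for the AUCs and Cmax. Section 7.3 defers analysis details to a separate statistical analysis plan.

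**The concern.** Two things look wrong on first reading. First, the condition refers in one place to Cohort B as a whole and in another to its first 4 subjects, which suggests two rules that could give different answers.

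Second, the 30% cutoff is set against an unnamed reference. CL/F is dose divided by AUC. If AUC shares the less-than-proportional rise in concentrations, CL/F in healthy subjects increases with dose, and the same 4 values could pass against one historical dose and fail against another. The mean, geometric mean and median of 4 values can also fall on different sides of a cutoff.

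The study is open-label, so these choices could in principle be made after the 4 values are known. At stake is whether 8 subjects with mild impairment, and any controls matched to them, are dosed in Part 1.

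**Working it through.** The plan gives no operating characteristics for this rule, and Section 7.1 says that the sample size is not power-based, so there is no stated figure to reproduce.

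**1. The two wordings.** The short statements give the condition without a cutoff, a number of subjects or a comparator. The longer sentence supplies all three and presents them as the definition. A general statement followed by its definition is one rule. The condition is also put as necessary: enrolment proceeds only if the first 4 subjects show the reduction. As written, a negative first look therefore keeps Cohort A closed, and no rule based on all 8 subjects competes with it.

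**2. The reference dose.** The documents give no size for the non-proportionality. Assume AUC proportional to dose^b with b = 0.9, 0.7 or 0.5. Then CL/F is proportional to dose^(1−b), and healthy CL/F at a historical dose D, relative to 600 mg, is f = (D/600)^(1−b). The cutoff is met when the true ratio at 600 mg is below 0.7 × f.

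| Reference dose | f (b = 0.9 / 0.7 / 0.5) | 0.7 × f | True reduction needed |
|---|---|---|---|
| 300 mg | 0.933 / 0.812 / 0.707 | 0.653 / 0.569 / 0.495 | 34.7 / 43.1 / 50.5% |
| 600 mg | 1 / 1 / 1 | 0.700 | 30% |
| 900 mg | 1.041 / 1.129 / 1.225 | 0.729 / 0.791 / 0.857 | 27.1 / 20.9 / 14.3% |

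For the chance of opening Cohort A, assume log-normal CL/F, a fixed historical value and the geometric mean of 4 subjects: P = Φ{[ln(0.7f) − ln(true ratio)] / (s/√4)}, with s = √ln(1 + CV²). For CV 30, 50 and 70% (assumed), s = 0.294, 0.472 and 0.631. Example, with a 600-mg reference, a true reduction of 40% and CV 50%: (ln 0.7 − ln 0.6) / 0.236 = 0.154 / 0.236 = 0.653, and Φ(0.653) = 0.743.

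| Reference dose | b = 0.9, CV 30 / 50 / 70% | b = 0.7, CV 30 / 50 / 70% |
|---|---|---|
| 300 mg | 72 / 64 / 61% | 36 / 41 / 43% |
| 600 mg | 85 / 74 / 69% | 85 / 74 / 69% |
| 900 mg | 91 / 80 / 73% | 97 / 88 / 81% |

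(All entries are for a true 40% reduction.) The spread is wide for b = 0.7 and much narrower for b = 0.9.

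**3. Which row applies.** Cohort B receives a single 600-mg dose with food. The plan derives CL/F only after a single dose. The one 300-mg regimen cited in healthy subjects is twice daily for 10 days and is mentioned for its tolerability, so the documents do not show a single-dose 300-mg reference at all. A 900-mg single dose was studied, but nothing suggests that a 600-mg result would be set against it without correction. Comparing like with like leads to the middle row, where f = 1 for every b and the cutoff is 30%.

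**4. The summary statistic.** Simulate 4 log-normal values and compare each statistic with the same statistic in healthy subjects. At a true 30% reduction, the geometric mean, arithmetic mean and median do not all agree in about 17, 20 and 24% of cases (CV 30, 50 and 70%). That is the worst place to look: with the truth on the cutoff, the geometric-mean rule is a coin toss (P = 0.5) at any CV. At a true 50% reduction the figures fall to 2, 8 and 14%, and the geometric and arithmetic means alone disagree in 0.5, 3.5 and 7%.

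**5. What the decision feeds.** The ANOVA in Section 7.3.1 compares each impairment group with matched controls from this study. The historical values do not enter it.

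**The case for a change.** The best case for a change is that an enrolment rule should be complete in the protocol, and that completing it costs a sentence. The data are open-label, the 4 values will be known when the reference is chosen, and the plan's own remark on dose proportionality shows that the choice is not neutral. Section 7.3.1 supplies no default statistic either: its geometric means do not extend to CL/F, while its group comparison is on the log scale. If 600 mg was meant, saying so is free.

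Much of this is right as description. The visible text names no reference and no statistic, and an analyst who took an uncorrected 900-mg reference would loosen the cutoff. But the harm needs a mismatched comparison that no section proposes. Healthy PK values may also stand in the redacted part of Section 1.1, in the cited investigator's brochure or in the separate analysis plan. Nor is writing it down entirely free: binding the rule to single 600-mg fed data gives up pooling across doses, which would leave a less precise reference if few healthy subjects were studied under those conditions.

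**Conclusion.** The concern does not call for a change. The two wordings are a statement and its definition, and the definition governs. The missing dose and statistic are a gap in detail that an analyst would fill by using healthy subjects given a single 600-mg dose, for whom the dose shift is zero whatever the degree of non-proportionality. The larger figures (an effective cutoff anywhere from 14% to 51%) arise only with a mismatched reference dose and an assumed exponent of 0.9 to 0.5, neither of which the documents supply. The choice of statistic matters mainly when the true reduction is close to 30%, where 4 subjects cannot settle the question under any statistic.

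The consequence is confined to opening Cohort A. The moderate and severe comparisons with matched controls stand as planned. This conclusion assumes that historical single-dose 600-mg data exist or that another dose would be corrected for. The visible documents do not confirm either, and a cross-reference to the historical data would be a courtesy to the reader, not a correction.
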